2.7 Framework

A superiority hypothesis testing framework is assumed. For the main outcomes, the following comparisons are planned:

a) Difference in AUC (concentration over time) of circulating carotenoid (lycopene) in the plasma TRL fraction:

1. Protein containing meal 1 vs. control meal
2. Protein containing meal 2 vs. control meal
3. Protein containing meal 1 vs. protein containing meal 2

b) Difference in AUC (concentration over time) of circulating carotenoid (beta-carotene) in the plasma TRL fraction:

4. Protein containing meal 1 vs. control meal
5. Protein containing meal 2 vs. control meal
6. Protein containing meal 1 vs. protein containing meal 2

As a secondary outcome:

c) Difference in AUC (concentration over time) of triglycerides in the plasma:

1. Protein containing meal 1 vs. control meal
2. Protein containing meal 2 vs. control meal
3. Protein containing meal 1 vs. protein containing meal 2
- 4.

d) Difference in AUC (concentration over time) of total carotenoids in the plasma:

5. Protein containing meal 1 vs. control meal
6. Protein containing meal 2 vs. control meal
7. Protein containing meal 1 vs. protein containing meal 2

2.8 Timing of final analysis

All outcomes will be analysed collectively after the end of the study (12-18 months after study start).

Figure 6 Time plan of the whole study and duration of the individual study phases. Trial refers to the time of whole-day clinical visits of the subjects to the CIEC. Extended period of recruitment and enrolment are optional, depending on the successful recruitment of the targeted 24 male subjects.

2.9 Timing of outcome assessments

Blood samples for outcome assessment will be collected at the following moments of the study:

- a) at time point 0h on visit days and
- b) post prandial timed blood draws (time points: 2h, 3h, 4h, 5h, 6h, 8h, 10h after meal intake).

3. Statistical Principles

3.1 P- values and multiplicity adjustment

As two statistical tests will be performed per main outcome (beta-carotene and lycopene), the total number of comparisons will be 6 (3 x 2) and therefore multiplicity correction will be applied. A Bonferroni corrected p-value will be used at that level: $\frac{\alpha}{2} = \frac{0.05}{2} = 0.025$. For the three post-hoc tests within each outcome (test meals vs. control), Tukey's post hoc test will be applied.

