2.6 Sample Size

It is assumed that two different outcomes will be tested as dependent variables and all pairwise comparisons will be performed. First lycopene and then beta-carotene will be tested. This will lead to three statistical tests per carotenoid readout: with the original alpha risk of 0.05 the corrected alpha risk would then be $0.05/6=0.083$ i.e. 0.83%. The Bonferroni adjustment will be used to keep the family-wise error at the specified error level and thus with the total number of pairwise comparisons equal to 6 each pairwise test is at the two-sided 0.83% significance level.

Area under the time – carotenoid concentration is assumed as main outcome for the sample size calculation.

When there are 2 outcomes (lycopene and beta-carotene), 3 treatments and a sample size of 4 in each of the 6 sequences, a 6x3 Williams Crossover inequality test of paired differences will have 96% power to detect a minimum difference of 4% of the area under time curve (AUC) (difference between 20% and 24% of AUC) or greater, assuming that the standard deviation of the paired differences is 4% at the 0.83% significance level. This leads to a total sample size of N=24 participants.

In case of one drop-out per sequence (n=3 per sequence), the power will reduce to 83%, which will still provide sufficient statistical strength. Sample size calculation was performed in nQuery 8 (version 8.3.1.0).

[figure not shown]

Figure 3 Power (%) vs. Sample Size per Sequence; minimum difference = 4%, SD = 4%, significance level = 0.8%

Figure 4 Power (%) vs. Minimum Expected Difference; n per sequence = 4, $SD = 4\%$, significance level = 0.8%

[figure not shown]

Figure 5 Power (%) vs. Standard deviation; $n=4$ per sequence, mean difference = 4%, significance level = 0.8%

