5.2 Analysis methods

The primary endpoint, AUC of either lycopene or beta carotene will be analysed using a linear mixed model using randomization sequence and treatment (test meal) as fixed terms and patient within sequence as a random term taking into account the cross-over design as described in chapter 5 of "Cross-Over Trials", Senn (2002). Baseline will be included as a co-variate.

Assumptions of normality and equality of variance will be verified by normality plots and boxplots, respectively. If data is non- normally distributed, log transformation will be attempted.

Non-parametrical analysis (Friedman tests followed by Wilcoxon- Mann- Whitney test) may be chosen in case data is not normally distributed, if log-transformation is not successful, though based on earlier studies data normally follows normal distribution.

The secondary endpoints - triglycerides, and if feasible additional carotenoids (see 5.1 above) will be analysed by the same methodology.

A linear mixed model will be first performed for each main outcome, with either baseline corrected AUC of lycopene or beta-carotene as the observed, dependent variable, and randomization sequence, test-meal as the independent variable (fixed factor) and patient within sequence as random factor. Pairwise comparisons of the intervention will be performed by means of Tukey's post-hoc test. Additionally, sensitivity analysis with the original outcomes (lycopene or beta-carotene) as dependent, randomization sequence, test meal and baseline concentration of the outcome as fixed factors and patient within sequence as random factor. 95% confidence intervals will be reported for the main outcomes.

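### The six primary contrasts carry three different significance rules, and nothing says whether the SAP's adjusted rule replaces the protocol's unadjusted one

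*SAP*

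**What the plan says.** SAP 2.7 lists six primary contrasts, three for lycopene and three for beta-carotene. Each set of three ends with "Protein containing meal 1 vs. protein containing meal 2". The significance rule for these contrasts appears in four places.

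- **SAP 2.6 (Sample Size).** On the count: "This will lead to three statistical tests per carotenoid readout". On the method: "The Bonferroni adjustment will be used to keep the family-wise error at the specified error level", so that "each pairwise test is at the two-sided 0.83% significance level". The same paragraph prints 0.05/6 as 0.083 and then, correctly, as 0.83%.
- **SAP 3.1 (P-values and multiplicity adjustment).** It opens: "As two statistical tests will be performed per main outcome (beta-carotene and lycopene), the total number of comparisons will be 6 (3 x 2"). It then divides alpha by two, giving 0.025 per carotenoid, and assigns Tukey's test: "For the three post-hoc tests within each outcome (test meals vs. control").
- **SAP 5.2 (Analysis methods).** "Pairwise comparisons of the intervention will be performed by means of" Tukey's test, with no alpha given. It adds: "95% confidence intervals will be reported for the main outcomes".
- **Protocol 11 (Statistical Analysis).** A repeated-measures ANOVA for each carotenoid, Fisher's protected LSD if the F test is significant, and a two-tailed 0.05 threshold. No step adjusts across lycopene and beta-carotene.

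Two further passages bear on precedence. SAP 2.1 refers the reader to the protocol for procedures that the SAP does not cover. The power calculation in Protocol 13 says that the sample size leaves room to adjust individual contrasts for multiplicity, but names no method.

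**The concern.** SAP 2.6 sets a family-wise error target over all six contrasts. The protocol rule does not meet it. With three meals, the F gate of the protected LSD holds the error at 5% within one carotenoid, but nothing controls it across two.

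A lycopene or beta-carotene contrast could therefore be positive under Protocol 11 and negative under both SAP rules, and either report could cite a pre-specified document. The available text does not say which result the plan had fixed in advance.

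The slips in SAP 3.1 make its own rule harder to read. It speaks of two tests per outcome where SAP 2.6 and 2.7 have three. It glosses the three post-hoc tests as test meals against control, which describes only two contrasts and leaves out protein 1 against protein 2.

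**Working it through.** **Inputs from the documents.** Overall alpha 0.05; 2 carotenoids; 3 pairwise contrasts each; N = 24 (4 in each of 6 sequences) or 18 (3 in each); difference 4; SD of paired differences 4; stated power 96% and 83% (all SAP 2.6). Tukey at 0.05/2 = 0.025 (SAP 3.1). F-protected LSD at 0.05 (Protocol 11).

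**Assumption.** Residual df for the contrasts of 46, that is (24 − 1) × (3 − 1). With period terms it would be 44, and the p-bands below do not change.

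**1. The plan's own figures.** 0.05/6 = 0.00833, or 0.83%, so 0.083 is a tenfold misprint. Power is taken from a two-sided noncentral t with noncentrality √N × 4/4 and df = N − 6.

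| Per-contrast rule | N = 24 (18 df) | N = 18 (12 df) |
|---|---|---|
| Stated in SAP 2.6 | 96% | 83% |
| 0.83% | 96.2% | 83.5% |
| 8.3% (the misprint) | 99.8% | 98.7% |
| Tukey at 0.025 | 96.7% | 85.6% |

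The calculation therefore used 0.83%. The df of N − 6 were chosen because they reproduce the stated power. With 46 and 34 df, power at 0.83% would be 98.1% and 91.7%.

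**2. The threshold under each rule, at 46 df.**

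| Rule | Critical value of \|t\| | Per-contrast p |
|---|---|---|
| SAP 2.6, Bonferroni over six | t(1 − 0.05/12) = 2.757 | 0.0083 |
| SAP 3.1, Tukey at 0.025 | q(0.975; 3, 46)/√2 = 2.711 | 0.0094 |
| Protocol 11, LSD | t(0.975) = 2.013, after F > 3.20 | 0.05, subject to the F gate |

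The two SAP rules disagree only for p between 0.0083 and 0.0094, a band about 0.001 wide.

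**3. Where the protocol and the SAP disagree.** Let t be the largest of the three contrasts, with balanced data. F is smallest, t²/2, when the third mean lies midway between the other two. It is largest, 2t²/3, when the third mean equals one of them. The critical value is F(0.95; 2, 46) = 3.20.

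- t²/2 = 3.20 gives t = 2.530, p = 0.0149. At or below this p the F test is always significant.
- 2t²/3 = 3.20 gives t = 2.191, p = 0.0336. Above this p the F test is never significant.

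So if a carotenoid's largest contrast has p between 0.0094 and 0.0149, it is always positive under Protocol 11 and negative under both SAP rules. From 0.0149 to about 0.034 the same can happen, depending on the third mean.

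Example: p = 0.012 gives t = 2.616. The Tukey-adjusted p is 0.032, above 0.025. F lies between 2.616²/2 = 3.42 (p = 0.041) and 2 × 2.616²/3 = 4.56 (p = 0.016), so the LSD step is open and the contrast passes it.

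**4. Family-wise error over both carotenoids, no true effect.** Simulation of 200,000 trials per setting, 24 subjects, 3 meals, 2 outcomes. The correlation between carotenoids is assumed, since the documents give none.

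| Rule | Correlation 0 | 0.5 | 0.8 |
|---|---|---|---|
| SAP 2.6, 0.83% each | 4.4% | – | – |
| SAP 3.1, Tukey at 0.025 | 4.9% | – | – |
| Protocol 11 | 9.6% | 9.1% | 8.0% |

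Within one carotenoid the protocol rule gives 4.9%, so the excess comes from testing two outcomes. Under independence the exact value is 1 − 0.95² = 9.75%, and the simulated 9.6% is scatter around it. With 18 subjects (34 df) the protocol rule gives 9.7%, 9.2% and 8.0%.

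**The case against.** The strongest reply is that the intended rule can be recovered. SAP 3.1 is the section devoted to multiplicity, SAP 5.2 repeats Tukey, and SAP 2.1 sends the reader to the protocol only for what the SAP leaves out. The power text in Protocol 13 anticipates an adjustment, which the SAP then supplies. SAP 2.6 can be read as planning, and planning at 0.83% while testing with a slightly less strict Tukey rule does no harm. The misprint is corrected in its own sentence. Title pages are not in the text available for review, so a statement of precedence may have stood there.

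Much of this is fair. The SAP rules are close, the misprint is harmless, and a statistician would probably follow SAP 3.1. But that precedence is inferred: no available passage says the SAP replaces Protocol 11, and the allowance in Protocol 13 does not appear in Protocol 11 as a step. SAP 2.6 is also worded as a testing rule, not only as a planning value.

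Three qualifications to the size also stand:

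- Independence gives nearly the worst case. Both carotenoids come from the same meal and the same TRL sample, so positive correlation is plausible; at 0.8 the protocol figure is 8.0%.
- The bands assume that the same p-value enters every rule. The two documents also differ on log-transformation and on whether subject is fixed or random, so the p-values themselves may differ.
- The 0.034 edge needs equal standard errors. The baseline covariate and subjects with only two visits would blur it.

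**Conclusion.** The concern holds. The same six primary contrasts have three written significance rules, and the text does not say which one decides. Within the SAP the conflict is close to nil (0.0083 against 0.0094). Between the SAP and Protocol 11 it matters: about 8% to 9.75% family-wise error against a 5% target, and a band of p-values (0.0094 to 0.0149 always, up to about 0.034 sometimes) in which the conclusion depends on the document followed. These figures rest on 46 residual df, balanced data and the assumed correlations. The 0.083 misprint and the miscounts are editorial, and N = 24 stands. This should be fixed before the analysis, but it does not threaten the design.

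**What to change.** State one rule in SAP 2.6, 3.1 and 5.2: for each carotenoid, Tukey-adjusted p-values for the three contrasts of SAP 2.7, significant if below 0.025. Then:

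- Say explicitly that this replaces the protected-LSD rule at 0.05 in Protocol 11.
- In SAP 2.6, correct 0.083 to 0.0083, and note that the 0.83% used for planning is slightly conservative for the Tukey rule, so N = 24 is unchanged.
- In SAP 3.1, change two tests per outcome to three, and describe them as all pairwise comparisons of the three meals.
- In SAP 5.2, if the planned 95% intervals are ordinary intervals for meal differences, label them descriptive and add simultaneous 97.5% Tukey intervals that match the test. This item is a refinement; the rest of the fix does not depend on it.

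The cost is wording only, with no change to N, visits or samples. The matching intervals, if added, are about 35% wider than ordinary 95% intervals (2.711/2.013 = 1.35).

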3.2 Adherence and protocol deviations

The adherence to the intervention will be assessed based on the combined entry in the participant's study log-book, which each participant will fill out. Deviations will be discussed between the PI, CIEC and statistician and decisions for removal of subjects and collected data from the study be discussed on a case-by-case scenario. Deviations will be :

- a) Not fasting at least 10 h overnight
- b) Eating something in the morning before any of the test-meals served at the LIH.
- c) Not consuming the entire test meal within a maximum of 30 minutes.
- d) Not conducting any washout before the study.
- e) Dropping out after the first clinical day

When subjects have completed successfully at least 2 clinical visits (any 2 out of 3), their data will be analysed, if the permission from the subject is granted.

Minor deviations from the protocol that will therefore be tolerated (not dropping out):

- Drinking water during the overnight fasting
- Eating carotenoid containing foods during the washout-period, as long as the individual food items in question are listed in the volunteer's booklet
- Up to 2 missing time-points (any 2 out of 8) during the clinical days.

3.3 Analysis population

The population is healthy adult males, living in Luxembourg, and the intervention will follow the intention to treat standard. The ITT population is all patients randomized to a diet or control arm whatever the arm they were finally allocated. The Per Protocol population is all patients randomized and allocated to an arm that followed strictly the protocol. Participants with major deviations to the protocol will be excluded from the PP population.

4. Trial Population

4.1 Eligibility

Twenty-four male individuals from or living in the region of Luxembourg will be recruited for this study. The reason for recruiting male subjects only is that carotenoid plasma concentrations are likely influenced by the monthly cycle of women [29], and we preferred not to undergo any risk in this regard – this position was also accepted by the FNR (Grant CAROPROT, C16/BM/11320230).

Inclusion criteria:

- healthy and free living;
- men;
- age between 20 and 50 years old;
- Body-Mass-Index (BMI) <30 kg/m²
- non-smokers (abstinent for more than 2 years);

Exclusion criteria:

- suffering from any metabolic disease that may cause digestive disturbances (such as Crohn's disease or colitis);
- malabsorption disorders;
- BMI over 30 kg/m²;
- hyperlipidaemia (triglycerides and total cholesterol over 200 mg/dl)
- any individuals following a special diet that is not compatible with wash-out periods or test meals (vegetarian, gluten-free or diabetic);
- regular consumption of more than 5 portions (80-100 g) of fruits and vegetables per day;
- being on medical treatment or consuming any medication for chronic conditions or recent illness (e.g. antibiotics);
- consuming regularly dietary supplements;
- abnormally high or low values of plasma circulating carotenoids;
- tobacco smoking;
- frequent alcohol consumption (over 2 glasses per day);
- food allergies or intolerances that are not compatible with test meals (e.g. gluten or milk intolerance);
- daily practice of intense physical activity of 120 min or more.

No special population group such as prisoners, children, the mentally disabled or groups whose ability to give voluntary informed consent may be in question, will be recruited for this study.

4.2 Recruitment

Recruitment period

Three to twelve months will be dedicated to the recruitment of the candidates for the study. However, this period might have to be extended if the initial foreseen period is not sufficient to recruit the total number of participants or in case of a high percentage of drop-outs.

During the recruitment period, male subjects interested in participating in the study will have the opportunity to register at the CIEC by phone, e-mail or regular mail. The staff of the CIEC will contact the registered candidates by phone to briefly explain the project, schedule an appointment for an information session, and send out a copy of the "Participants' information sheet" so that interested candidates have the opportunity to carefully read the project's description and experimental procedure, prior to signing the "Informed Consent Form".

Enrolment period

The enrolment period will develop over a foreseen period of up to twelve months, with the possibility of extending this period in case of necessity. The enrolment period will involve: a) a session where

selected participants will be fully informed about the study, have the opportunity to pose any questions they might have, sign the “Informed Consent form” and fill out the “Health&Lifestyle questionnaires”; b) the selection of eligible candidates based on the results from the questionnaires; and c) a screening visit to collect a blood sample (20 ml) and urine sample (ca. 10-20 ml).

4.3 Withdrawal/ follow-up

Participants are free to withdraw from the study at any moment if they desire to do so. However, we will try our best in terms of follow-up to keep subjects in the study. Any participant showing new medical problems that are not easily explained (e.g. colds) or that requires the use of medication (e.g. antibiotics) will be withdrawn from the study.

Subjects that have at least completed 2 clinical days will be kept for statistical analysis, and given that subjects agree to keeping their data. Otherwise, the cases will be removed from analysis.

4.4 Baseline patient characteristics

Anthropometric parameters

During the enrolment phase, the candidate will be measured for the following:

- height
- weight
- waist and hip circumference
- waist-to-hip ratio
- percentage of body fat as calculated by bioelectrical impedance analysis (BIA)

Urine sampling

During the enrolment phase, candidates will be asked for a urine sample for screening of any metabolic disorder that might be an exclusion criterion (e.g. diabetes) and that the candidate is not aware of or was not mentioned in the Health&Lifestyle questionnaire.

Urine will be tested for standard urine analysis parameters such as

- Glucose
- Ketones
- ascorbic acid
- pH (GAK Combi Screen Plus 9, Analytikon, Hennigsdorf, Germany)

Blood sampling

Blood samples will be collected during the enrolment phase; prior to the beginning of the initial washout period and at time point 0h on visit days.

Continuous baseline variable will be described using the total number of samples, mean, SD (standard deviation) and median for the total sample. Categorical and binary variables will be described by number of cases in each category and percentage.

5. Analysis

5.1 Outcome definition

Primary outcomes:

Beta-carotene and lycopene

Beta-carotene and lycopene will be measured in the plasma triacylglycerol rich lipoprotein (TRL) fraction in μM at baseline (0h) and 2h, 3h, 4h, 5h, 6h, 8h, 10h after test meal intake. Using non-compartmental analysis, repeated measures over time of carotenoids will be summarised as postprandial AUC (trapezoidal approach) using the PK functions plug-in for Microsoft Excel and will be validated in a statistical software such as R or SAS system. Of note, it is planned to baseline-subtract all further concentrations (hours 2-10), and to also subtract potentially occurring negative values from the AUC.

Baseline concentrations will be included as co-variates into the linear mixed model.

Secondary outcomes:

Triglycerides

Triglycerides will be measured in the plasma in mg/dL at baseline (0h) and 2h, 3h, 4h, 5h, 6h, 8h, 10h after test meal intake. Using non-compartmental analysis, repeated measures over time of triglycerides will be summarised as postprandial AUC (trapezoidal approach) using the PK functions plug-in for Microsoft Excel and will be validated in a statistical software such as R or SAS system.

Minor abundant carotenoids:

Isomers of beta-carotene and lycopene will be treated as the all-trans native form, i.e. all chromatographic peak area will be combined if isomers are identified in the plasma-TRL fraction.

If alpha-carotene or other carotenoids such as lutein and beta-cryptoxanthin can be measured (if chromatographic sensitivity is sufficient), AUC in the TRL fraction will also be determined, as described for beta-carotene and lycopene.

They will be accounted for in the analyses as secondary outcomes with similar analysis methodology

Total carotenoids will be produced by summing up all carotenoids measured and analysed as the primary endpoint

Carotenoids after colonic digestion:

Native carotenoids after colonic digestion, as well as excreted degradation products such as apo-carotenoids will be investigated, as far as the analytical capabilities allow. As no previous data exists in this respect, this part will be of highly explorative character.

5.2 Analysis methods

The primary endpoint, AUC of either lycopene or beta carotene will be analysed using a linear mixed model using randomization sequence and treatment (test meal) as fixed terms and patient within sequence as a random term taking into account the cross-over design as described in chapter 5 of "Cross-Over Trials", Senn (2002). Baseline will be included as a co-variate.

Assumptions of normality and equality of variance will be verified by normality plots and boxplots, respectively. If data is non- normally distributed, log transformation will be attempted.

Non-parametrical analysis (Friedman tests followed by Wilcoxon- Mann- Whitney test) may be chosen in case data is not normally distributed, if log-transformation is not successful, though based on earlier studies data normally follows normal distribution.

The secondary endpoints - triglycerides, and if feasible additional carotenoids (see 5.1 above) will be analysed by the same methodology.

A linear mixed model will be first performed for each main outcome, with either baseline corrected AUC of lycopene or beta-carotene as the observed, dependent variable, and randomization sequence, test-meal as the independent variable (fixed factor) and patient within sequence as random factor. Pairwise comparisons of the intervention will be performed by means of Tukey's post-hoc test. Additionally, sensitivity analysis with the original outcomes (lycopene or beta-carotene) as dependent, randomization sequence, test meal and baseline concentration of the outcome as fixed factors and patient within sequence as random factor. 95% confidence intervals will be reported for the main outcomes.

